6.1 Inclusion criteria

- Adolescent or young adults (12-24 years old).
- Receiving inpatient, day care or outpatient treatment
- Diagnosed with AN, or atypical AN, according to DSM-5.

- Patients have gained <2 kg within at least one month of TAU. Outpatients should have attended ≥4 therapeutic sessions. 2 kg within the time frame of at least one month appears most appropriate to predict further therapy response or non-response to the current treatment according to our systematic review and meta-analysis on early response and treatment outcome prediction [84].
- The patient can read and write in English.
- Written Informed consent to participate

6.2 Exclusion criteria

Exclusion criteria:

- Serious self-harm, suicidality, psychotic disorder, serious medical comorbidities (as detailed below) which are contraindications for olanzapine
- Current alcohol or illicit drug use disorder
- On major tranquilliser or opioids
- QTc interval >450 ms (two separate ECG measurements) [47]
 - A QTc interval >500 ms in the ECG or rises by more than 60 msec from baseline or other severe cardiac side effects will stop study participation of this patient.
 - A QTc interval >500 ms in the ECG or rises by more than 60 msec from baseline or other severe cardiac side effects in more than one patient in the feasibility study will lead to a stop of the study.

Alerting liver function tests or white blood cell count [47]

- \circ Bilirubin >40 μ mol/L
- Alkaline phosphatase >200 U/L
- AST >80 U/L
- ALT >90 U/L
- GGT >90 U/L
- \circ WBC <2.0 x10⁹/L
- $\circ \quad MCV > 120 \ fL$
- On other psychopharmacological medication at stable dose for <4 weeks
- On medication interacting with olanzapine
- Pregnancy
- Of childbearing potential and unwilling to have pregnancy tests.
- Objecting to taking effective contraceptive measures as specified under section 8.10. on trial restrictions. The participant information and consent sheet include a section on pregnancy and appropriate birth control measures.
- Breast feeding
- Insufficient understanding of the Trial/lack of capacity to agree to the Trial procedures as assessed by the responsible clinician
- Hypersensitivity to Olanzapine or to any of its excipients
- Taking part in another pharmacological trial for AN
- Involvement in research that includes contraindications for treatment with olanzapine

Serious self-harm means one of the following:

• Recent (within the last 12 months) self-harm with suicidal intent

Page 29 of 60

- Recent self-harm with the risk to a person's own life (e.g., drug intake, deep cutting, burning, swallowing sharp items)
- Recent self-harm which could lead, or has led, to long lasting impairment of one's health and functioning

Serious medical comorbidities which are contraindications for olanzapine mean one of the following:

- Coronary heart disease
- Cerebrovascular disease
- Parkinson's disease, parkinsonism or dementia
- Hepatic or renal impairment

We will examine and document all physical and mental comorbidities that are not exclusion criteria. For example, mood disorders, obsessive-compulsive disorder, anxiety disorders and personality disorders are common co-morbidities which are not exclusion criteria.

In order to determine inclusion and exclusion criteria, to detect serious physical or mental illnesses, and to find out current medications or potentially needed medication, a full psychiatric and medical history taking, physical examination and assessment will take place when screening potential participants, including:

- Body weight and height
- Blood pressure and pulse rate, lying and standing
- Body temperature
- Muscle strength
- Skin
- Signs of infection and nutritional deficiency
- Alcohol, Smoking and Substance Involvement Screening Test (ASSIST) for study participants >15 years old; all participants will be screened for alerting levels of GGT and MCV as indicators of alcohol use; alcohol and drug use is a health risk for people on olanzapine [85]

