One reason for the NIHR HTA call for a study testing antipsychotics in young people with eating disorders is the discrepancy between EDs treatment guidelines and clinical practice. Whereas treatment guidelines such as NICE do not recommend psychopharmacological treatment, between 80% and 90% of patients with EDs are taking psychopharmacological drugs. Instead of taking medications without EDs indication and without monitoring, this open-label feasibility study will test olanzapine in a well-defined patient group. Olanzapine is a medication approved for the treatment of schizophrenia, and its risk profile is well-known. However, if olanzapine is added to psychotherapy, it might lead to a slightly increased risk of adverse events.

Despite being licensed for Schizophrenia, Olanzapine is already in use in patients with treatment-resistant anorexia nervosa [43], it has been tested successfully in randomized-controlled trials [30], and it is

Page 20 of 60

recommended for weight gain in people with anorexia nervosa with category grade B evidence by the WFSBP guidelines on the pharmacological treatment of eating disorders World Federation of Societies of Biological Psychiatry (WFSBP) guidelines for the pharmacological treatment of eating disorders [98]. We will manage the risk by excluding patients with a specifically high risk. People with pregnancy, women of child bearing potential not willing to do a pregnancy test and not willing to adhere to contraceptive measures as specified under section 8.10 (Trial restrictions), people with serious self-harm, suicidality, psychotic disorder, serious medical comorbidities which are contraindications for olanzapine, current alcohol or illicit drug use disorder, on major tranquilliser or opioids, QTc interval >450 ms (two ECG measurements), alerting liver function tests or white cell count [47], on other medication at stable dose for <4 weeks, on medication interacting with olanzapine are considered as high risk. We will use appropriate guidance and instructions for QTc measurement in the same standardised way throughout the trial. The instructions will cover things like the same level of activity before ECG measurements (e.g., sitting or lying after two minutes rested), that if both readings are significantly different, then rather than take an average, redo with a different machine. We will also take consideration of factors such as age, gender, potassium levels, family history, and cardiac examination results.

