7.1.2 Screening

The aim of the screening process is to ascertain whether inclusion and exclusion criteria are met. In accordance with the inclusion and exclusion criteria outlined in section 6.1. and 6.2., the clinical research team will update the eCRF with the following information about the potential participant after informed consent is obtained:

- Age
- Gender
- Diagnosis of AN
- Level of nonresponse to TAU (at least one month of treatment; weight gain <2 kg within at least one month of TAU; outpatients should have attended ≥4 therapeutic sessions.
- Potential serious self-harm, suicidality, psychotic disorder
- Serious medical comorbidities which are contraindications for olanzapine
- Current alcohol or illicit drug use disorder
- Use of major tranquilliser or opioids
- QTc time
- Liver function tests or white cell count
- Use of other medication at stable dose for <4 weeks
- Use of medication potentially interacting with olanzapine
- Pregnancy test, willingness to take further pregnancy tests after 8 weeks, 16 weeks, 6 months, and 12 months and to take contraceptive measures as specified in section 8.10. on trial restrictions (females of childbearing potential only)
- Breast feeding
- Capacity of the adult participant or the adolescent participant and their legal representatives to agree to the study

For definition of serious self-harm and serious medical comorbidities see section 6.1. and 6.2.

To obtain this information and thus determine inclusion and exclusion criteria, a full psychiatric and medical history taking, physical examination and assessment will take place. See section 6.1. and 6.2. To obtain this information is included in the standard care for a patient with AN if pharmacological treatment is considered.

Page 31 of 60

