8.8 Known drug reactions and interaction with other therapies

The current recommended therapeutic elements to treat AN are psychotherapy, diet counselling and physical monitoring. Thus, there is no specific combination or concomitant medication to be expected in the patient group of this study.

The following combinations are, in principle, known to lead to potential drug interactions:

- Diazepam: May potentiate orthostatic hypotension.
- Alcohol: May potentiate orthostatic hypotension. Alcohol dependence is an exclusion criterion of this trial. Patients will be advised not to drink alcohol during the trial.
- Carbamazepine: Increased clearance of olanzapine.
- Fluvoxamine: May increase olanzapine levels.
- CNS Acting Drugs: Caution should be used when taken in combination with other centrally acting drugs and alcohol.
- Antihypertensive Agents: Enhanced antihypertensive effect.
- Levodopa and Dopamine Agonists: May antagonize levodopa/dopamine agonists.
- Lorazepam (IM): Increased somnolence with IM olanzapine.
- Other Concomitant Drug Therapy: When using olanzapine in combination with lithium or valproate, we will refer to the Drug Interactions sections of the package insert for those products.

Fluoxetine is available in a fixed combination with olanzapine (Symbyax®). This combination is indicated for the treatment of depressive episodes associated with bipolar I disorder or treatment resistant depression. In adolescents, the daily dose should be below 12 mg. However, in this trial 10 mg olanzapine is the maximum daily dose.

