8.9 Concomitant medication

Caution is advised for the drugs listed in the previous section as concomitant medication. However, there is no contraindication for the monotherapy with olanzapine. Additionally, blood concentration of olanzapine will be monitored throughout the study. Contraindications according to the BNF apply to elderly patients who will not be included in this trial and to patients who receive olanzapine as intramuscular application which is not envisaged in this trial either.

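### Section 6.2 excludes patients on drugs that interact with olanzapine, while 8.8 and 8.9 allow the listed interacting drugs with caution, so eligibility depends on the section a site applies

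*Protocol*

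**What the plan says.** Three sections treat an interacting drug as a reason not to enrol, or as something to screen for.

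- Protocol 6.2 lists as an exclusion "On medication interacting with olanzapine". It names no drugs and sets no level of interaction.
- Protocol 2.4 describes the patients to be left out on grounds of risk and ends that list with "on medication interacting with olanzapine are considered as high risk".
- Protocol 7.1.2, the information recorded at screening, has a wider item: "Use of medication potentially interacting with olanzapine".

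Two sections treat such drugs as usable alongside olanzapine.

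- Protocol 8.8 introduces its list with "The following combinations are, in principle, known to lead to potential drug interactions". The entries are diazepam, alcohol, carbamazepine, fluvoxamine, centrally acting drugs as a class, antihypertensives, levodopa and dopamine agonists, intramuscular lorazepam, and lithium or valproate. For lithium or valproate it provides for use together with olanzapine by reference to the package inserts.
- Protocol 8.9 then says: "Caution is advised for the drugs listed in the previous section as concomitant medication".

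Two further places bear on the question. Another 6.2 criterion excludes patients "On other psychopharmacological medication at stable dose for <4 weeks", which by implication accepts those stable for longer. Protocol 3.6.1 plans to record concomitant medication and to explore whether commonly taken additional drugs alter the action of olanzapine.

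**The concern.** The two groups of sections give opposite answers for the same patient, and nothing in the protocol ranks one above the other. A clinician working from the exclusion criteria turns the patient away. A clinician working from the treatment section enrols the patient and takes care.

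Two things are at stake. The first is safety: 2.4 puts these patients among those at specifically high risk, while 8.9 handles them by caution alone. The second is what the study measures. It is multicentre (section 5), section 10.2 says that it tests recruitment, and section 10.3.2 puts the numbers approached, screened and included under the main outcome. If sites differ in how they read the criterion, those counts mix two eligibility rules.

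**Working it through.** No figure in the protocol is in dispute here. The check is a comparison of sections, followed by an illustration of size.

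**Step 1: is 8.8 the list that 6.2 refers to?** Section 6.2 names no drugs, so the overlap rests on reading 8.8 as the protocol's list of interacting drugs. It is the only such list, and its introduction speaks of potential interactions, which matches the wording of the screening item in 7.1.2. The reading is reasonable, but it remains an inference.

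**Step 2: take three patients through the sections.**

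| Patient | 6.2 interaction criterion | 6.2 stable-dose criterion | 8.8 and 8.9 |
|---|---|---|---|
| Lithium, stable for 4 weeks or more | excluded | accepted | used together, package insert, caution |
| Another centrally acting drug, stable for 4 weeks or more | excluded, if the class entry counts | accepted | caution |
| Antihypertensive | excluded | not addressed | caution |

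Every row holds a conflict between 6.2 and 8.8 to 8.9. The first two also hold one inside 6.2: if the class entry in 8.8 defines what interacts, the interaction criterion leaves the stable-dose allowance almost nothing to act on.

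**Step 3: does any other section settle it?** No. Section 3.6.1 presumes that participants take additional drugs that may interact, which fits 8.9. Section 2.4 sides with exclusion.

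**Step 4: possible size.** Let s be the share of otherwise eligible and willing patients who take a drug listed in 8.8. The protocol does not give s, so the values below are assumptions. The target of 55 comes from sections 4 and 10.2.

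- If the listed drugs are allowed with caution, 55 such patients give 55 enrolments.
- If the listed drugs exclude, the number needed is 55 / (1 − s), rounded up:
  - s = 10%: 55 / 0.90 = 61.1, so 62
  - s = 20%: 55 / 0.80 = 68.75, so 69
  - s = 30%: 55 / 0.70 = 78.6, so 79
  - s = 50%: 55 / 0.50 = 110

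Over the six planned recruitment months (2 to 7), this is 55 / 6 = 9.2 a month under caution, against 62 / 6 = 10.3 at s = 10% and 110 / 6 = 18.3 at s = 50%.

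**The case against.** The strongest reply is that 6.2 governs entry and 8.8 to 8.9 govern drugs started during treatment. The alcohol entry in 8.8 makes such a split: dependence is named as an exclusion, and abstaining is advice for the trial period. For the other drugs, however, the protocol never states the split. Sections 8.8 and 8.9 are not limited to drugs begun after entry, and the lithium and valproate text is not so limited either. The reply shows one way in which the text could be repaired; it does not show that the text is consistent.

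A second reply is that no site would read 6.2 so strictly as to bar every psychotropic drug. This largely stands. The adjacent stable-dose criterion would have almost no purpose, section 6.2 says that common mood, anxiety and obsessive-compulsive comorbidities do not exclude, and 3.6.1 expects additional medication. The realistic ambiguity is therefore mainly about the agents that 8.8 names.

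A third reply is that much of the damage could be traced afterwards. Section 7.1.2 records use of potentially interacting drugs for consented patients, 3.7 records concomitant medication at screening, and the trial summary plans screen-failure information. This also stands, so the protocol does not support an inference that the counts would be useless for planning an RCT. What those records would not show is selection before consent, when psychiatrists identify patients under 7.1.1.

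**Conclusion.** The contradiction is real: for a patient on a stable dose of a listed drug, the protocol states both exclusion and use with caution. It depends on reading 8.8 as the list behind 6.2, for which the document offers no alternative. It affects safety and the comparability of screened and included counts between sites. Its size is unknown; the range of 62 to 110 against 55 rests entirely on an assumed share of 10% to 50%.

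Two stronger inferences are tempting and should not be drawn.

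- Section 2.4 states that "between 80% and 90% of patients with EDs are taking psychopharmacological drugs", and a reader might conclude that 6.2 rules out most of the target population: 55 / 0.20 = 275 to 55 / 0.10 = 550 patients for 55 enrolments. That rate covers all eating disorders and all psychotropic drugs. Section 6.2 already removes patients on major tranquillisers and those on recently changed psychotropics under either reading, so the rate does not describe otherwise eligible patients. The calculation also needs every psychotropic to exclude, which the rest of 6.2 makes implausible.
- A reader might set the same rate against the remark in 8.8 that "there is no specific combination or concomitant medication to be expected". The remark follows from the recommended elements of treatment and concerns a specific drug or combination. It can mean that no particular drug belongs to standard care, and it need not mean that patients take nothing.

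**What to change.** Reconcile sections 2.4, 6.2, 7.1.2, 8.8 and 8.9.

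- Give each drug or class listed in 8.8 one status: excluding at entry, or allowed with caution.
- State whether 8.8 and 8.9 apply at entry or only to drugs started during treatment.
- Make the status of centrally acting drugs agree with the stable-dose criterion in 6.2.
- Use the same wording in 2.4, 6.2 and 7.1.2, including whether potential interactions count.

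Which drugs fall on which side is a clinical decision for the sponsor, and this review takes no position on it. The cost is a protocol wording amendment and a note to sites. No new data field is needed, because screening and medication data are already to be collected, and the sample size does not change.

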7 TRIAL PROCEDURES

7.1 Recruitment

Recruitment will take place at specialist CAMHs and adult eating disorder units in inpatient, outpatient, and day care settings.

7.1.1 Participant identification

Psychiatrists in the participating ED services will identify patients in their care for potential eligibility, approach them and inform them the study. If patients agree, their verbal agreement will be documented in the patient notes, and their contact data will be forwarded to the researcher of the OPEN study. The researcher will inform the patient and the medical doctor or psychiatrist who is responsible for the patient's treatment in detail about the study and the necessary screening. Thus, the aims of the participant identification process are to find and approach potential participants and bring the clinicians and the potential participants in contact with the study team. We will also recruit participants by advertising posters in each of the trial sites. This will open the study to a diverse pool of candidates and minimize the potential of selection bias by consultant psychiatrists.

Page 30 of 60

In light of the COVID-19 pandemic, contingency plans will be put in place to ensure the study will be completed in the scheduled time frame and the patient safety not jeopardized. In addition to the hard copies of consent and PI forms, all consent forms and PI forms will be made available online for use as appropriate in the event that such measures become necessary Trial assessments will take place in person adhering to social distancing guidelines, and qualitative assessments will take place virtually or in-person based on the participants preference. The Trial Management Group (TMG) Trial Steering Committee (TSC), and the Data Monitoring and Ethics Committee (DMEC) will all meet for sessions virtually to ensure the safety of the members.

Qualitative interviews will examine the decision-making process among an estimated 30 participants who either agree or decline to participate in the trial. After consent to participate in OPEN has been obtained or declined, participants will be given a participant information sheet for the qualitative interview and asked for verbal consent to be contacted by the qualitative research assistant who will follow up with a phone call to answer questions and schedule one-off appointments.

7.1.2 Screening

The aim of the screening process is to ascertain whether inclusion and exclusion criteria are met. In accordance with the inclusion and exclusion criteria outlined in section 6.1. and 6.2., the clinical research team will update the eCRF with the following information about the potential participant after informed consent is obtained:

- Age
- Gender
- Diagnosis of AN
- Level of nonresponse to TAU (at least one month of treatment; weight gain <2 kg within at least one month of TAU; outpatients should have attended ≥4 therapeutic sessions.
- Potential serious self-harm, suicidality, psychotic disorder
- Serious medical comorbidities which are contraindications for olanzapine
- Current alcohol or illicit drug use disorder
- Use of major tranquilliser or opioids
- QTc time
- Liver function tests or white cell count
- Use of other medication at stable dose for <4 weeks
- Use of medication potentially interacting with olanzapine
- Pregnancy test, willingness to take further pregnancy tests after 8 weeks, 16 weeks, 6 months, and 12 months and to take contraceptive measures as specified in section 8.10. on trial restrictions (females of childbearing potential only)
- Breast feeding
- Capacity of the adult participant or the adolescent participant and their legal representatives to agree to the study

For definition of serious self-harm and serious medical comorbidities see section 6.1. and 6.2.

To obtain this information and thus determine inclusion and exclusion criteria, a full psychiatric and medical history taking, physical examination and assessment will take place. See section 6.1. and 6.2. To obtain this information is included in the standard care for a patient with AN if pharmacological treatment is considered.

Page 31 of 60

7.1.3 Payment

Patients will be paid £10 for consenting to take part in the study and £10 for completing the study after one year. This covers travel costs and other costs. However, we do not expect patients to travel specifically for the study. Participant payment of £20 will be offered to those who decline to enter the trial to support participation in qualitative interviews. Differential incentive payments for qualitative research can be offered to advance the goals of a study (Persad et al, 2019).

7.2 Consent

The CI will have overall responsibility for the conduct of research. The CI will ensure that any person delegated responsibility to participate in the informed consent process is duly authorised, trained and competent to participate according to the ethically approved protocol and principles of Good Clinical Practice (GCP) and Declaration of Helsinki.

Informed consent will be obtained prior to the participant undergoing the baseline assessments.

Written consent will be taken by the members of the research team at each site. The Patient Information and Consent forms will be given to the participants and ample time will be given for the participants to review and complete the forms and for any questions to be answered. One copy of the signed consent forms will be given to the patient, one copy will be kept in the patient medical notes and one copy will be filed in the Site File.

The right of a participant to refuse participation without giving reasons must be respected, and the participant will remain free to withdraw at any time from the trial without giving reasons and without prejudicing his/her further treatment and will be provided with a contact point where he/she may obtain further information about the trial. This contact point will be the researcher and the CI.

Data and samples collected up to the point of withdrawal will only be used after withdrawal if the participant has consented for this. This is explained in the information sheet and specified in the consent form. Patients under 16 years old will be required to assent to take part in the trial and a consent from a parent/legal guardian will be obtained. Participants who turn 16 years old during the study will be required to consent, and it is the responsibility of the PI to ensure this is done in a timely manner. The PI will take responsibility for ensuring that all participants are protected and participate voluntarily in an environment free from coercion or undue influence.

We will only include patients who can read and write in English.

Before asking patients to participate in the trial, the potential adult participant or the potential adolescent participant and their parents or legal representatives will have a discussion with their medical doctor or consultant psychiatrist about the therapeutic effects and potential side effects of the treatment with olanzapine. They will explain the following common and very common side effects for olanzapine according to the BNF: Anticholinergic syndrome; appetite increased; arthralgia; asthenia; eosinophilia; fever; glycosuria; oedema; sexual dysfunction. Psychiatrists will receive training on how to explain these common and very common side effects once trial sites are open to adhere to uniform of clinical explanations with the participants. These side effects are also outlined in the consent form and patient information form in both an electronic and physical copy.

Participants will be informed that the use in this study is off-label. Patients and their families or legal representatives will receive a leaflet about olanzapine and about the study. The leaflet will be approved by the REC and be in compliance with GCP, local regulatory requirements and legal requirements. They will have the opportunity to ask questions.

Page 32 of 60

All members of the research team who will have contact with study participants will have received adult and child safeguarding training.

The capacity assessment during the screening process will be conducted by the clinical teams on site and include an assessment that the potential adult participant or adolescent participant and their parents/legal representatives have the ability to:

- understand the information of the participant information sheet, particularly regarding the effects and potential side effects of olanzapine, the procedures at each study visit and the participant's right to withdraw from the study at any time with no negative implications to their clinical care;
- understand the purpose and nature of the research
- understand what the research involves, its benefits (or lack of benefits), risks and burdens
- understand the alternatives to taking part
- are able to retain the information long enough to make an effective decision.
- Weigh up the options (taking olanzapine or not, taking part in the study or not) and are able to make a free choice
- are capable of making this particular decision at the time it needs to be made (though their capacity may fluctuate, and they may be capable of making some decisions but not others depending on their complexity)
- are capable of communicating their decisions.

Mental capacity will be assumed lacking if, in a specific circumstance, a person is unable to decide for him or herself because of impairment or a disturbance in the functioning of their mind or brain. This trial will include children (under the age of 16 years of age), young people (between the ages of 16 and 17) and adults. Therefore, the legal framework and ethical considerations for involving young people in research which are set out in the Department of Health Reference Guide to Consent for Examination or Treatment (2009) apply. Olanzapine is considered to be of significant value of children and young people with AN. The protection of participating children is fully considered.

These aspects of the Capacity assessment are to be documented in the CRF at each study visit.

Where a participant becomes incapacitated during the trial, the patient will be withdrawn from the study.

